**Short Title**

PENG Block versus LP Block for Postoperative Analgesia after Anterior Total Hip Arthroplasty

**Full Title**

Peri-capsular Nerve Group Block versus Lumbar Plexus Block for Postoperative Analgesia after Primary Anterior Approach Total Hip Arthroplasty

**Sponsor or Funding Source**

Departmental funding

**Summary/Purpose/Rationale**

Regional anesthesia procedures represent a common modality for postoperative analgesia after total hip arthroplasty surgeries (THA). The standard practice at our institution for many years has been the Lumbar Plexus block (LPB), which anesthetizes the L1-L5 lumbar nerve roots. While the LPB offers analgesia from the associated sensory block, it also blocks motor fibers, leading to lower extremity weakness that could potentially delay the patient's ability to participate in early physical therapy and may thereby delay discharge. In the past several years, newer regional anesthesia block approaches have been described and investigated in an attempt to provide patients with postoperative analgesia while avoiding associated muscle weakness, facilitating earlier physical therapy participation and discharge. One such nerve block is the peri-capsular nerve group (PENG) block, which anesthetizes the articular branches of the femoral, obturator, and accessory obturator nerves providing sensory innervation to the hip joint capsule without consistently causing lower extremity weakness. While we continue to perform LPB for postoperative analgesia after THA at our institution, some institutions are utilizing the PENG block to provide postoperative analgesia and facilitate early mobilization. There are currently no prospective studies that directly compare the efficacy of LPB to PENG block for providing postoperative analgesia after THA.

**Objectives**

The purpose of this randomized, double blinded, prospective study is to compare the postoperative analgesia provided by the PENG block to that provided by the LPB for patients undergoing primary anterior approach THA. We hypothesize that the PENG block will provide equivalent analgesia to LPB after THA. The primary outcome will be a comparison of patient-reported numeric rating scale (NRS) pain scores with movement at six hours following block placement. Equivalency will be defined as a difference of less than one point in either direction on the eleven-point NRS pain scale (0-10). Secondary outcomes will include NRS pain scores with movement at 12, 18, and 24 hours, NRS pain scores at rest at 6, 12, 18, and 24 hours, time to first opioid administration, cumulative dose of postoperative opioid administration within the first 24 hours, motor strength at six hours after block placement as assessed by straight leg raise on a six-point scale (0-5), and distance walked at first postoperative physical therapy session. The 18 hour assessment for pain at rest and with movement is allowed to be done retrospectively at the time of the 24 hour assessment, as this time point would end up interrupting the sleep of the study subject as would be occurring in the early morning hours. If the subject reports asleep

at the 18 hour scheduled time point, the no pain score will be obtained. This will be considered a missing data point and not a deviation. If the subject reports they were awake at the 18 hour time point, then a pain score at rest will be obtained but if the subject reports no movement, this score will be a missing data point and not a deviation.

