Nurses will chart vital signs and medication administration in the electronic medical record (EMR) as per our standard protocol. Research personnel will measure patient-reported NRS pain scores at rest and with movement for each time by patient interaction, either face to face, or by calling the patient's room or phone numbers. This will include the primary outcome of patient-rated pain with movement of the surgical extremity on the NRS pain scale at six hours after block placement (roughly correlating to two hours after arrival to their room) as well as secondary outcomes that include but are not limited to pain at rest and with movement at 12, 18, and 24 hours following block placement, and strength to straight leg raise at six hours post-block placement. The cumulative 24 hour opioid consumption will be abstracted from the EMR for doses received while admitted, and documented by the patient in their pain journal and abstracted via phone call after their discharge, if this occurs prior to 24 hours after the block. Physical therapists will also document their encounters in the EMR, including but not limited to the secondary outcome of distance ambulated during their first session in feet. These metrics will be accessed, abstracted, de-identified, and analyzed by research personnel who are blinded to group allocation.

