### **Data Analysis**

Demographic information will be collected and compared between the groups to verify that randomization balanced out important baseline variables between LPB and PENG. For the primary outcome of patient-reported pain with movement at six hours after block placement, the equivalence hypothesis test of LPB versus PENG groups will be performed using two one-sided t-tests. We will also calculate a point and confidence interval estimate of the difference between LPB and PENG groups. Secondary outcomes will also be compared using t-tests and confidence intervals.

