### **Missing Data Points**

If we find that study participants are missing substantial parts of their sequence of longitudinal measurements (6, 12, 18, and 24 hours), we will employ a mixed effects modeling framework that allows us to use all available data to test hypotheses about differences between PENG and

LRB at each time point. Models will be implemented using the ‘lme4’ package in R statistical software.

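### Distance walked is measured at the first therapy session whenever that occurs, so a difference between arms in session timing could mask or reverse a difference in walking

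*Combined protocol and SAP*

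**What the plan says.** All references are to the combined protocol and SAP.

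- **Objectives** names "distance walked at first postoperative physical therapy session" as the last item in the list of secondary outcomes. **Measurements** has it taken from the therapists' notes in the electronic record, as "the secondary outcome of distance ambulated during their first session in feet". Neither section gives a clock time or window for the session.
- **Summary/Purpose/Rationale** describes LPB as also blocking motor fibers, "leading to lower extremity weakness that could potentially delay the patient's ability to participate in early physical therapy". It describes the newer blocks as meant to avoid weakness, "facilitating earlier physical therapy participation and discharge".
- **Data Analysis** states: "Secondary outcomes will also be compared using t-tests and confidence intervals". Session time plays no part in that comparison.
- **Missing Data Points** offers a mixed model for the 6, 12, 18 and 24 hour series only. It does not reach the walking outcome.
- The other secondary outcomes are anchored in time. Pain has four fixed hours, opioid dose runs to 24 hours, time to first opioid is itself a time, and the plan measures "motor strength at six hours after block placement as assessed by straight leg raise".

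No section makes time to first session an outcome or names session time for collection. None says what distance is recorded for a patient who is deferred or cannot walk.

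**The concern.** The walking outcome is tied to an event, not to a time after the block. The plan's own rationale allows that the timing of this event may depend on the treatment. Suppose that some patients in one arm are not ready on the afternoon of surgery and are first seen the next day. They are then measured when more of the block has worn off and may walk further than patients seen early. An advantage in early mobilization would show up as earlier sessions, which the plan does not analyse, and not as longer distances, which it does.

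This is the only walking outcome in the trial. Without session times by arm, a null or reversed distance result could mean that the blocks are alike for mobilization, or that the arms were measured at different stages of recovery. The report could not tell these apart.

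**Working it through.** **What can be recomputed.** The plan gives no mean, SD or session time for distance, so it has no figure of its own on this point. Its only sample-size figure concerns the primary outcome, and it reproduces. With SD 2.0, margin 1, one-sided 0.05 and 80% power, n = 2 × (2.0 × (1.645 + 1.282) / 1)² = 68.5, or 69 per arm. The present point does not touch that calculation.

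**Can timing vary?** Measurements equates six hours after the block with roughly two hours after arrival in the room, so arrival is at about four hours. Objectives places the 18 hour point in the early morning. By inference, blocks are placed between morning and about midday, and patients reach their rooms in the afternoon or thereabouts. A first session on the same day or the next day is then possible. Nothing in the documents fixes or equalizes this.

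**Illustration 1: deferral to the next day.** All inputs are assumptions: same-day mean 60 ft for PENG and 40 ft for LPB (a true same-day deficit of 20 ft), next-day mean D in deferred patients, and a fraction q of LPB patients deferred. No PENG patient is deferred.

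LPB mean = (1 − q) × 40 + q × D. The deficit vanishes at q = 20 / (D − 40).

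| D (ft) | LPB − PENG at q = 10% | LPB − PENG at q = 30% | q at which the deficit vanishes |
|---|---|---|---|
| 150 | 51 − 60 = −9 | 73 − 60 = +13 | 20/110 = 18% |
| 100 | 46 − 60 = −14 | 58 − 60 = −2 | 20/60 = 33% |
| 80 | 44 − 60 = −16 | 52 − 60 = −8 | 20/40 = 50% |

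If 10% of both arms are deferred to 150 ft, the means are 0.9 × 60 + 15 = 69 and 0.9 × 40 + 15 = 51, a deficit of 18 ft. The 2 ft lost is not a timing bias. It arises because the deferred tenth is assumed to walk equally far in both arms.

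**Illustration 2: gradual recovery.** Suppose that walking capacity rises r ft per hour, LPB is P ft worse at the same clock time, and LPB sessions are d hours later on average. The observed difference is −P + r × d, which is zero at d = P / r. For P = 20 ft, that is 6.7 h at r = 3, 4 h at r = 5 and 2 h at r = 10. With r = 5, an 8 hour delay gives −20 + 40 = +20 ft in favor of the weaker arm. With d = 0, the full −20 ft is seen.

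Both models agree: the distortion depends on the difference in timing between arms and is absent when there is none.

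**The case against.** The strongest reply is that delayed ability is not a delayed session. No section says that therapy waits for motor recovery or is put off for weakness. Leaving the recovery unit depends on resolution of the spinal, which both arms receive. If therapists come on a routine schedule and weak patients walk few or no feet, the outcome captures weakness in the right direction. This stands: the bias is conditional on sessions being deferred differently by arm, which the documents neither state nor exclude.

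Three stronger readings are tempting, and the documents do not support them.

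- A reader might infer that the plan expects LPB to delay therapy, so that the outcome rewards delay. The rationale says only that weakness could potentially do so, as background.
- A reader might infer that a reversed result is likely. The reversal in Illustration 1 needs a high assumed next-day distance and deferral confined to one arm. At 80 ft and 10% deferral, 16 of the 20 ft remain.
- A reader might infer that LPB weakness would go undetected, or that distance is the trial's main test of mobilization. Motor strength is measured at six hours, when all patients are said still to be admitted. The stated hypothesis concerns analgesia only.

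What the reply does not remove is the gap itself. Strength on a leg raise is not walking, and no other part of the plan would show whether the distances were measured at comparable times.

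**Conclusion.** The point holds in conditional form. The distance comparison can be attenuated or reversed if first sessions are deferred more often, or occur later, in one arm, and the plan as written would not reveal it. If timing is equal by arm, there is no bias. The size cannot be derived from the documents. In the assumed scenarios, a 20 ft same-day deficit disappears at between 18% and 50% one-sided deferral, and is nearly unchanged (18 ft) when 10% of both arms are deferred.

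The consequence is limited to one secondary outcome. The primary outcome, its sample size and the six-hour strength measure are unaffected. The change is still worth making, because it is cheap and protects the only walking result from being misread.

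**What to change.** Leave therapy scheduling as it is and change only what is abstracted and how it is analysed.

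1. Seek the time of the first session in the therapy notes already being abstracted. Report time from block to first session by arm as a companion outcome.
2. Define the outcome as distance at the first session within one window, stated in hours after block placement and fixed before unblinding. A limit such as the end of the day of surgery would not do, since it gives morning and later cases different amounts of time.
3. Score as 0 ft patients who were seen in the window but could not walk, and those deferred for weakness or unresolved block. Treat other absent sessions as missing in the main analysis.
4. Compare arms with a rank-based test, because of the zeros.
5. Because reasons for deferral may be poorly recorded, add two sensitivity analyses: all patients with no session in the window scored as 0 ft, and then all of them as missing.

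Adjusting distance for session time should not replace this. Session time arises after randomization and may be affected by the block, so such adjustment belongs among the sensitivity analyses at most.

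The cost is slightly more abstraction (session time and reason for deferral) and an effect estimate less simple than a difference in means.

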## **Methods/Measurements**

### **Design**

This will be a randomized, double blinded, equivalency trial that will take place after approval from our Institutional Review Board. Written informed consent will be obtained from all study participants prior to randomization. The trial will be registered on clinicaltrials.gov before any enrollment begins.

### **Selection Criteria**

Inclusion: Adults between 18 and 90 years of age undergoing elective primary total hip arthroplasty surgery by an anterior approach at Atrium Health Wake Forest Baptist Davie Medical Center, and who have consented to and lack any contraindications to either LPB or PENG block for postoperative analgesia will be recruited for participation in the study.

Exclusion: Patients with any contraindications to regional anesthesia, such as history of allergy to amide local anesthetics, pre-existing coagulopathy or thrombocytopenia (less than 100,000 per microliter), refusal to either analgesic block, presence of a progressive lower extremity neurological deficit, localized or systemic infection, chronic use of high dose opioid analgesics (defined as daily use greater than 60mg oxycodone equivalents), as well as those who are pregnant, will be excluded from participation. A diagnosis of multiple sclerosis and Parkinson's disease will also exclude potential study subjects. Any patients who refuse enrollment or withdraw their consent will be excluded and any of their information already collected will be destroyed.

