## **Study Protocol**

### **Baseline data collection**

Upon arrival and check-in to the regional anesthesia area of surgical services at Davie Medical Center on the day of surgery, enrolled patients will be asked to rate their baseline verbal pain score both at rest and with movement on the eleven-point NRS pain scale (0-10, where 0 represents no pain and 10 represents the worst imaginable pain). Patient characteristics will be recorded, including age, gender, height, weight, BMI, surgeon, and operative side, as well as preoperative opioid use and doses. Baseline motor function will be assessed by straight leg raise on the surgical side to resistance and measured on the six-point Medical Research Council (MRC) scale (0-5, where 0 represents no voluntary contraction possible, 1 represents muscle flicker without movement of limb, 2 represents active movement only with gravity eliminated, 3 represents movement against gravity but without resistance, 4 represents movement possible against some resistance, and 5 represents normal motor strength against resistance).

Two phone numbers will be obtained from the patient, if the patient consents, for contact after discharge. Each patient will also be provided with a pain journal with which to document pain scores for any remaining time points after discharge, in case they are not available by phone at the time points of interest. All patients will still be admitted at the six hour mark, for collection of the primary endpoint of NRS pain with movement, as well as motor strength at six hours after block placement.

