## Measurements

Following the completion of surgery, all subjects will be brought to the post-anesthesia care unit (PACU) for recovery, where they will recover until satisfactory resolution of spinal block as judged by an attending anesthesiologist is shown. Subjects will then be transported to an inpatient room, where nurses will monitor their vital signs and pain scores regularly. Subjects will receive standard of care pain medications for postoperative pain management as indicated. Subjects will continue to receive scheduled acetaminophen 1000mg every six hours (or 15mg/kg if their weight is below 65kg), and the NSAID administered preoperatively (either celecoxib 200mg twice daily or meloxicam 15mg once daily) barring any contraindication such as renal impairment or vascular disease. Oxycodone every four hours may also be administered as needed with dose ranges determined by the Davie Medical Center perioperative surgical home anesthesiologist consulted for postoperative care, or another narcotic at equipotent dosages if they have a contraindication to oxycodone. Alternatively, they may receive combination products such as Percocet (oxycodone/acetaminophen) or Vicodin/Norco (hydrocodone/acetaminophen) instead, with the acetaminophen dosage adjusted accordingly. All

opioids will be converted to oxycodone equivalents to allow for appropriate comparison using a widely available dose conversion table.

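### Preoperative opioid dose is recorded but not used in the analysis of 24-hour opioid consumption, so this secondary comparison is less precise than it could be

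*Combined protocol and SAP*

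**What the plan says.** All references are to the combined protocol and SAP.

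- **Selection Criteria.** The opioid exclusion is "chronic use of high dose opioid analgesics (defined as daily use greater than 60mg oxycodone equivalents"). Chronic users at or below 60 mg/day are eligible.
- **Baseline data collection.** The patient characteristics to be recorded end with "as well as preoperative opioid use and doses".
- **Objectives.** The secondary outcomes include "time to first opioid administration, cumulative dose of postoperative opioid administration within the first 24 hours".
- **Measurements.** On the source of the total: "The cumulative 24 hour opioid consumption will be abstracted from the EMR for doses received while admitted". After discharge, doses come from the patient's journal and a phone call. All "opioids will be converted to oxycodone equivalents to allow for appropriate comparison using a widely available dose conversion table". The only postoperative opioid order described is as-needed: "Oxycodone every four hours may also be administered as needed with dose ranges determined by the Davie Medical Center perioperative surgical home anesthesiologist", with an equipotent or combination product as substitute. Continuation of a home opioid is not mentioned.
- **Data Analysis.** "Secondary outcomes will also be compared using t-tests and confidence intervals". No covariate, subgroup or sensitivity analysis uses preoperative opioid. Demographic information is compared between arms, but nothing follows from an imbalance.
- **Randomization.** Allocation is in blocks by numbered envelopes. No stratification by opioid use is stated.

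**The concern.** Postoperative opioid is given as needed, so two arms can reach similar pain scores with different amounts of it. The 24-hour total is the outcome that would show this, and its precision matters for interpreting a finding of equivalent pain.

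The eligible population runs from patients who take no opioid to patients who take up to 60 mg/day. If preoperative dose predicts postoperative consumption, part of the between-patient spread in the 24-hour total has nothing to do with the block and could be explained by a variable already in hand. An unadjusted t-test leaves that spread in the error term. Users may also be few: at an assumed 5-10% of 80 patients, 4 to 8 per arm are expected. A split that differs by several patients is then plausible, and the planned analysis has no means of correcting for it.

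**Working it through.** **1. The plan's own figure.** The Power Analysis gives a margin of 1 point, SD 2.0, significance level 0.05 and power 80%. For two one-sided tests with a true difference of zero:

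n = 2 × [SD × (z₀.₉₅ + z₀.₉₀) / margin]² = 2 × [2.0 × (1.645 + 1.282) / 1]² = 68.51, rounded up to 69 per arm.

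This reproduces the stated 69 (t-based power at 69 per arm is 79.9%). It concerns pain with movement at six hours and involves no opioid quantity, so nothing below alters it. The protocol states no SD, power or margin for either opioid endpoint.

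**2. Inputs for the 24-hour total.** None is in the protocol, so all are assumptions:

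- share of patients who are regular users, p: 5%, 10%, 20%
- mean home dose among users, μ, with SD σ equal to half the mean: 20 (SD 10) or 30 (SD 15) mg/day
- SD of all other 24-hour opioid use, s: 15 or 20 mg
- home dose adds to other use and is independent of it
- 80 patients per arm, the recruitment target

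**3. Formulas.**

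- Added variance V = p(σ² + μ²) − (pμ)²
- SE ratio, unadjusted to adjusted = √(1 + V/s²). Under the additive model, adjustment removes V, apart from one degree of freedom.
- Share of effective sample lost = V/(V + s²)
- SD of the arm difference due to home dose alone = √(2V/80)

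**4. Results.**

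| p | μ (σ) | V | SE ratio, s = 20 | SE ratio, s = 15 |
|---|---|---|---|---|
| 5% | 20 (10) | 25 − 1 = 24 | 1.03 | 1.05 |
| 5% | 30 (15) | 56.25 − 2.25 = 54 | 1.07 | 1.11 |
| 10% | 20 (10) | 50 − 4 = 46 | 1.06 | 1.10 |
| 10% | 30 (15) | 112.5 − 9 = 103.5 | 1.12 | 1.21 |
| 20% | 20 (10) | 100 − 16 = 84 | 1.10 | 1.17 |
| 20% | 30 (15) | 225 − 36 = 189 | 1.21 | 1.36 |

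The lowest ratio is √(1 + 24/400) = 1.03, and 24/424 = 6% of the effective sample is lost. The highest is √(1 + 189/225) = 1.36, and 189/414 = 46% is lost. The chance shift in the arm difference has an SD of √(2 × 24/80) = 0.8 mg to √(2 × 189/80) = 2.2 mg. That shift is the same variance seen another way and does not come on top of the wider interval.

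**5. A different dose distribution.** With home dose uniform on 0-60 mg and s = 20 mg, V is 0.05 × 1200 − 1.5² = 57.75 at 5% users and 0.30 × 1200 − 9² = 279 at 30%. The variance factors are 1.14 and 1.70, so the confidence interval is 7% to 30% wider. With s between 10 and 30 mg, the variance factor runs from 1.06 to 3.79. The result depends heavily on s.

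**6. Without a continued home regimen.** The gain then depends only on the correlation r between preoperative dose and the 24-hour total, with SE ratio 1/√(1 − r²). The two ends in step 4 correspond to r² = 24/424 = 0.057 (r = 0.24) and r² = 189/414 = 0.457 (r = 0.68). If r were zero, nothing would be gained or lost.

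**The case against.** The strongest case for leaving the plan alone has four parts.

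*The magnitude is assumed.* The protocol gives no share of users, home dose or opioid SD. The 36% combines the highest share, the higher dose and the smaller SD; the low end is 3%. If a home dose replaces as-needed doses, the effect shrinks; if tolerance raises need, it grows. This stands, and it is why only a range can be given.

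*The consequence is limited.* Both opioid endpoints are secondary, with no margin and no power claim. Allocation is random, and the planned confidence interval would honestly reflect the extra variance. This also stands: the cost is imprecision, not an invalid comparison.

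*Preoperative dose is already collected and could be inspected.* This does not answer the point. Recording a variable does not use it, and an adjustment chosen after the arms have been compared would be post hoc.

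*Total opioid is a defensible endpoint.* A reader might infer something stronger: that both endpoints score habitual home opioid as need arising from the block, so that a patient on 60 mg/day registers about 60 mg despite perfect analgesia, and that the endpoints should therefore count as-needed doses only. The protocol does not support this. It never says that a scheduled home opioid continues after surgery, and it does not label the total as attributable to the block. Time to first opioid depends on one dose, not on every dose. A home dose also acts on surgical pain, so restricting the endpoint would discard real analgesic exposure and change what is estimated. After discharge, patients would have to classify their own doses. The objection succeeds against that reading, but adjusting the unchanged total avoids it.

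**Conclusion.** The point holds as a matter of efficiency. Users up to 60 mg/day are eligible and their dose is recorded, yet the 24-hour total is to be compared without it. If preoperative dose predicts consumption, which is plausible but not shown in the protocol, the planned analysis gives up precision and leaves chance imbalance in a few users uncorrected. Under the assumptions in the working, the standard error is about 3% to 36% larger than it need be. That range illustrates the possible size and is not an estimate for this trial.

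A reader might also infer bias toward one block. Randomization rules out a systematic effect of preoperative dose on the expected difference in the 24-hour total. For time to first opioid, an early habitual dose, if one were given, could end the interval whatever the block and so draw the arms together. Because the protocol is silent on continuation, that is a reason for a sensitivity analysis and not a demonstrated error. The primary outcome and the 69 per arm are untouched.

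**What to change.** In Data Analysis, before any unblinded comparison:

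1. Keep the total 24-hour dose in oxycodone equivalents as the endpoint.
2. Analyse it in a linear model with treatment and preoperative daily oxycodone equivalents (zero for non-users) as covariate. Report the adjusted difference and its confidence interval.
3. As a sensitivity analysis, report both the 24-hour total and time to first opioid in patients with no preoperative opioid use. This subset is defined at baseline, so the comparison within it remains randomized.

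The cost is two or three sentences and one degree of freedom. Screening against the 60 mg limit already requires a daily figure in oxycodone equivalents, so the covariate should exist. It should be converted with the same table as the postoperative doses. The sensitivity analysis uses fewer patients and is supportive only. No new data from patients, no extra patients, and no change to eligibility or opioid management are needed.
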